After providing informed consent and completing a baseline survey (see section V. A.), participants will be block-randomized in a 2:1 ratio to usual care with (N=200) or without (N=100) LCS navigation. The randomization scheme will be concealed from the study coordinator responsible for randomizing participants. Randomization will be stratified by smoking status (current/former), housing status (homeless/housed), prior discussion of lung cancer screening with their PCP, and primary clinical site where the patient sees their PCP (JYP vs. non-JYP sites) to ensure balance between study arms on these variables. We will stratify by smoking status (determined based on responses to the eligibility screener) because lung cancer risk perceptions and LCS motivations may differ between current and former smokers.^{75,76} Current smoking will be defined as having smoked all or part of a cigarette in the past 30 days.⁷⁷ We will stratify by housing status based on responses to various items within the baseline survey because the navigation needs of formerly homeless people in housing may differ from those who are currently homeless. Current homelessness will be defined in the following ways: a) usually staying in an emergency shelter, transitional shelter, abandoned building, place of business, car or other vehicle, church or mission, hotel or motel, or anywhere outside during the past 7 days, b) usually housed in last 7 days but cannot stay in a residence for at least 14 days, c) usually institutionalized in the last 7 days if the admission was less than 90 days and they were homeless prior to admission, or d) usually institutionalized in the last 7 days if the

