admission was more than 90 days and they have no identified residence where they can stay at least 14 days upon discharge. These definitions are concordant with definitions of homelessness used by the US Department of Health and Human Services (section 330 of the Public Health Service Act, 42 USC § 254b)⁷⁸ and by the US Department of Housing and Urban Development (S. 896 HEARTH Act of 2009).⁷⁹ We will stratify based on prior discussion of lung cancer screening with their PCP (defined by an item within the baseline survey) due to the fact that these participants are farther along in the lung cancer screening process. Finally, we will stratify by the patient's primary care clinical site since clinics may differ in their proximity to facilities that offer LCS or in their practice patterns around recommending and ordering LDCT for LCS. We will create 2 clinical site strata: 1 for JYP and one encompassing all of the 5 non-JYP study sites described above.

The 2 study arms are as follows:

Arm 1: Usual care **without** patient navigation (N=100). Participants assigned to this arm will be given basic educational materials on general lung health (Appendix K) and referred back to their PCP to discuss whether to pursue lung cancer screening per usual practice.

Arm 2: Usual care **with** patient navigation (N=200). Participants assigned to this arm will be informed about LCS, provided educational materials on LCS and patient navigation (Appendix L), and offered access to an LCS navigator. The navigator's principal role is to guide participants through the LCS process. The navigator's secondary role is to provide a brief tobacco intervention for participants who currently smoke. These roles are described below:

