Quantitative analysis: LDCT completion at 6 months (26 weeks) (1° outcome) and LDCT completion with timely diagnostic follow-up (2° outcome) are both binary outcomes. In the principal analysis, we will assess the difference between the navigation and usual care arms on attainment of these outcomes using the Chi-square test. We will also use logistic regression models to examine the associations between treatment condition and outcomes including clinical site and other known predictors of outcomes to increase the precision of effect estimates. Additional analyses will examine time to receipt of LDCT for LCS between study arms using time-to-event methods (log-rank tests and Cox regression models). Although we expect to be underpowered to detect significant interactions, we will examine whether the effect of navigation varies by smoking status, housing status, or clinical site in an exploratory analysis.

Qualitative analysis: Qualitative interviews will be audiotaped and transcribed. We will use inductive content analysis methods to identify major and minor themes, and we will use deductive methods to strengthen, refine, and enhance understanding of identified themes.¹⁰⁵ Qualitative data coding will be performed by 2 trained study staff members using NVivo 11 software. The data coders will meet regularly with Drs. [name] and [name] to discuss the structural thematic framework, categories, and coding plan. We will resolve discrepancies through discussion and comparison to raw data. Coding will continue iteratively until a high level of reliability ($Kappa>0.80$) is established.

Integration with quantitative data: Based on a mixed methods approach,¹⁰⁶ we will use the qualitative interview data to interpret and explain the quantitative observations from the trial. This will aid in better understanding why overall LDCT completion was higher or lower than

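### Randomisation is stratified on four factors, but the principal Chi-square uses none and the supporting model names only site; if the strata are prognostic, this costs about 0 to 4 points of power.

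*Combined protocol and SAP*

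**What the plan says.** Section IV.D (Treatment assignment): "Randomization will be stratified by smoking status (current/former), housing status (homeless/housed), prior discussion of lung cancer screening with their PCP, and primary clinical site" (JYP versus non-JYP). Each factor has two levels, so there are 16 cells. Allocation is 2:1, with 200 participants to navigation and 100 to usual care.

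The same section gives reasons for each factor. Prior discussion is included "due to the fact that these participants are farther along in the lung cancer screening process". Site is included because "clinics may differ in their proximity to facilities that offer LCS or in their practice patterns around recommending and ordering LDCT for LCS". The reasons for smoking and housing concern motivation and navigation needs, which is a weaker case that they predict completion.

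Section VI.C (Statistical Methods) makes this the principal analysis of both the primary and the secondary outcome: "we will assess the difference between the navigation and usual care arms on attainment of these outcomes using the Chi-square test". Logistic models are additional, "including clinical site and other known predictors of outcomes to increase the precision of effect estimates". An exploratory analysis asks "whether the effect of navigation varies by smoking status, housing status, or clinical site in an exploratory analysis". Prior discussion is named in none of these analyses.

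**The concern.** When randomisation is stratified on factors that predict the outcome, the arms are more alike on those factors than simple randomisation would make them. An unadjusted test takes its variance as if that balance were absent. It therefore rejects slightly too seldom under the null and loses some power under the alternative.

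The plan accepts the principle, since it adjusts for covariates to gain precision, but it confines that gain to a supporting model. That model names only one of the four factors and no test statistic. The phrase about other known predictors could cover the remaining three, so they are not excluded; they are simply not prespecified. Table 2 in section VI.A lists many baseline candidates, so the adjusted analysis could be settled after the data are seen.

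What is at stake is a modest amount of power and the credibility of the adjusted result. Validity is not in question.

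**Working it through.** **Inputs from the documents.** 5% in usual care and 15% with navigation (section VI.D); 100 and 200 participants; four two-level stratification factors. Expected events: 100 × 0.05 + 200 × 0.15 = 5 + 30 = 35.

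**Not in the documents, so assumed.** Two-sided 5% alpha, no dropout, blocks of 6, factor prevalences, and odds ratios (OR) for screening.

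**The plan's own figure.** Section VI.D states power above 80%. With the pooled Chi-square formula:

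- pooled rate = 35/300 = 0.1167
- SE under the null = √[0.1167 × 0.8833 × (1/100 + 1/200)] = 0.0393
- SE under the alternative = √[0.05 × 0.95/100 + 0.15 × 0.85/200] = 0.0334
- power = Φ[(0.10 − 1.96 × 0.0393)/0.0334] = 75.4%

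Exact enumeration of the uncorrected Chi-square gives 76.9%. The arcsine formula (80.3%), the unpooled formula (85.0%) and a one-sided pooled test (85.5%) all exceed 80%. As alpha and sidedness are not stated, the plan's figure is not called an error here. It does show that the named test, if two-sided at 5%, has no visible spare power.

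**Formula for the gain.** If the strata explain a share R² of outcome variance, multiply both SEs by √(1 − R²). Power is then 76.4% at R² = 2%, 77.8% at 5%, 79.3% at 8% and 80.2% at 10%: gains of 1.0, 2.4, 3.8 and 4.8 points.

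**Simulation.** Stratified permuted blocks, N = 300, prevalences 75/60/30/50% (smoking, housing, prior discussion, site), 12,000 runs per cell, Monte Carlo SE about 0.4 point for power and 0.2 for size. Power (%) for the primary outcome at 5% versus 15%:

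| Assumed prognosis | Chi-square | Site-only score | Four-factor score | Four-factor Wald | 16-stratum CMH |
|---|---|---|---|---|---|
| None | 78.0 | 78.1 | 78.3 | 75.7 | 77.6 |
| Prior discussion OR 3 | 77.4 | 77.4 | 78.7 | 76.3 | 77.9 |
| Prior discussion OR 3, site OR 2 | 77.9 | 78.2 | 79.6 | 77.2 | 78.7 |
| Prior discussion OR 4, others 1.5 | 77.0 | 77.1 | 79.3 | 77.3 | 78.6 |
| Prior discussion OR 6, others 2 | 78.5 | 78.8 | 82.4 | 80.3 | 81.4 |

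Against the Chi-square, row by row:

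- the four-factor score test gains 0.3, 1.3, 1.7, 2.3 and 3.9 points
- the site-only model gains 0.1, 0.0, 0.3, 0.1 and 0.3
- the four-factor Wald test changes power by −2.3, −1.1, −0.7, +0.3 and +1.8

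**Size** (nominal 5%):

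| Test | 10% vs 10% | 5% vs 5% |
|---|---|---|
| Chi-square | 3.8 to 4.8% | 4.4 to 4.8% |
| Four-factor score | 4.9 to 5.2% | 4.9 to 5.4% |
| Four-factor Wald | not run | 3.1 to 3.5% |
| Four-factor likelihood ratio | not run | 5.8 to 6.2% |

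Coverage of the 95% CI for the standardised risk difference at 5% versus 15% is 94.4 to 94.9%.

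**Sensitivity.** A second simulation (20,000 runs, prevalences 70/60/30/50%) moved from the Chi-square to the four-factor score test as follows: 77.2 to 77.5 with no prognosis; 77.6 to 78.9 with prior discussion OR 3; 78.1 to 79.9 with all ORs 2; 78.2 to 81.7 with all ORs 3; 78.2 to 82.3 with prior discussion OR 6 and others 2. Blocks of 3 and 12 gave similar gains. Only an extreme case (prior discussion OR 10, others 3) reached 6 to 7 points.

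**The case against.** No error is shown. The purpose stated for stratifying is balance, which the design delivers whatever the test. A 2×2 test is a legitimate principal analysis for a pragmatic trial, and it matches the marginal 5% versus 15% contrast used for power. The principal test has no covariates to choose, so the freedom to choose after the fact affects only the supporting model. All of this stands, and it is why the point concerns efficiency and prespecification only. A standardised risk difference keeps the marginal contrast.

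The size of the gain rests on assumed inputs. The top value needs OR 6 for prior discussion and OR 2 for smoking and housing, whose prognostic case is weaker. Under the two scenarios closest to the plan's own rationale, the gain is 1.3 and 1.7 points. If navigation works less well in those with prior discussion (treatment OR 0.4 times as large, an assumption), a 4,000-run simulation puts the gain at 0.9 instead of 1.8 points (OR 3 with site OR 2), and at 2.6 instead of 3.8 in the strongest scenario. This also stands: the gain shrinks but stays positive.

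The remedy depends on the choice of test, as the Wald and likelihood-ratio results show. A score test beside a delta-method CI also disagreed on significance in 5 to 7% of simulated trials. A Chi-square beside a Wald CI disagrees about as often, so this does not favour the current plan, but the CI method should be stated. The secondary outcome was not simulated.

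**Conclusion.** The concern holds. The principal analysis ignores all four stratification factors, and the supporting model fixes only one of them. If the factors do not predict screening, almost nothing is lost. If they do, the Chi-square gives up roughly 1 to 2 points under the plan's own rationale (prior discussion, with or without site) and up to about 4 if all four are strongly prognostic. Naming site alone recovers practically none of this. Type I error is not inflated.

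These figures assume two-sided 5% alpha, the prevalences and odds ratios shown, and no dropout; the main simulation uses blocks of 6. They are for the primary outcome, and the gains in the table assume a treatment odds ratio constant across strata. The prespecification gap does not depend on these assumptions.

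**What to change.** In section VI.C, before outcome data are examined:

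- Make the principal analysis of both outcomes a logistic model with treatment, smoking status, housing status, prior discussion and site, all named, as main effects only.
- Prespecify a score test of the treatment term. Avoid the default Wald test (it loses about 1 to 2 points when the factors are weak), the likelihood-ratio test (size about 6% when events are few) and a 16-stratum Mantel-Haenszel test (too many strata for about 35 events).
- Report the standardised risk difference with a 95% CI, and state how the interval is computed.
- Keep the unadjusted Chi-square as a sensitivity analysis.

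The cost is wording only, because the four factors must be recorded in order to randomise. There are downsides. With about 35 expected events, about 5 of them in usual care, the model cannot be extended beyond main effects. The score test may have to be requested explicitly in the software. The result is a little harder to explain than a 2×2 table.

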expected and why the navigation intervention did or did not improve these outcomes. Following from our stratified sampling scheme, we will integrate the quantitative and qualitative data by assessing for thematic differences in the interview content of participants who did (N=20) and did not (N=20) attain the primary outcome. We will focus in particular on comparing and contrasting these two groups' views on the utility of the navigator with respect to the Health Belief Model domains of perceived susceptibility, cues, self-efficacy, and barriers, as described above. We will additionally incorporate the quantitative baseline measures tapping these Health Belief Model domains into integrated analyses. Table 4 illustrates the way in which these quantitative and qualitative data elements will be integrated and presented in a blended fashion.

Table 4. Proposed integration of quantitative and qualitative data.

Health Belief Model domains	Measurement (method)	LCS LDCT at 6 months	
		Yes (N=20)	No (N=20)
Perceived susceptibility / severity	Baseline survey (quan)	Lung cancer risk perception, severity, and worry scores	
	Post-intervention interview (qual)	Quotes/themes about navigator impact on perceived susceptibility/severity	
Cues	Baseline survey (quan)	Past provider recommendation for LCS, exposure to LCS information	
	Post-intervention interview (qual)	Quotes/themes about navigator provision of cues for LCS	
Self-efficacy	Baseline survey (quan)	General and LCS-specific self-efficacy scores	
	Post-intervention interview (qual)	Quotes/themes about navigator impact on self-efficacy	
Perceived benefits / barriers	Baseline survey (quan)	LCS knowledge, competing subsistence difficulty scores	
	Post-intervention interview (qual)	Quotes/themes about navigator assistance with barriers	

D. Power Analysis

The sample size justification is based on the primary outcome of LCS LDCT completion at 6 months (26 weeks). Internal BHCHP data suggests a presently negligible baseline rate of LCS LDCT. Allowing for improvement in this rate as LCS comes into wider practice, we will assume that 5% of usual care (Arm 1) participants will obtain an LDCT within 6 months (26 weeks). In our judgment, increasing this completion rate to 15% would represent a clinically meaningful change. We will have >80% power to detect such a difference with a sample size of 200 in the navigation arm (Arm 2) and 100 in the usual care arm (Arm 1).

VII. RISKS AND DISCOMFORTS

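### The stated power of more than 80% is not met by the planned Chi-square test: at a two-sided 5% level it is about 77%

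*Combined protocol and SAP*

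**What the plan says.** Section VI.D (Power Analysis) rests the sample size on the primary outcome, completion of a screening LDCT within 26 weeks. It reports that "Internal BHCHP data suggests a presently negligible baseline rate of LCS LDCT", allows for some improvement in practice, and sets the usual care rate at 5%. For the navigation arm it holds that "increasing this completion rate to 15% would represent a clinically meaningful change". The conclusion is: "We will have >80% power to detect such a difference with a sample size of 200 in the navigation arm (Arm 2) and 100", where the last number is the size of Arm 1.

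Section IV.D (Treatment assignment) gives the same allocation: "participants will be block-randomized in a 2:1 ratio to usual care with (N=200) or without (N=100) LCS navigation".

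Section VI.C (Statistical Methods) fixes the test for the principal analysis: "we will assess the difference between the navigation and usual care arms on attainment of these outcomes using the Chi-square test".

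Neither section, nor any other part of the document, gives a significance level, one- or two-sided testing, a power formula or software. VI.C does not say which form of the Chi-square test is meant.

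**The concern.** A power figure has meaning only for a stated test at a stated level. Here the test is named and the level is not. Under the most usual reading, an uncorrected Pearson Chi-square test at two-sided 5%, the plan's own rates and arm sizes do not appear to reach 80%.

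This sentence is the only sample-size justification in the plan. If power is overstated, so is the reassurance that a null result would give about a difference the investigators call clinically meaningful. A reader cannot check the figure without the level and the method.

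**Working it through.** **Inputs from the plan.** Usual care: n₁ = 100, p₁ = 0.05 (VI.D). Navigation: n₂ = 200, p₂ = 0.15 (VI.D; sizes also in IV.D). Test: Chi-square (VI.C). No interim analysis is planned (IX.C), so no significance level is spent early.

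**Assumptions.** Two-sided 5% level (z = 1.96) and the uncorrected Pearson statistic. The plan states neither.

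**Step 1. Trying to reproduce the stated figure with the normal formula for the Pearson test.**

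- Pooled rate: (100 × 0.05 + 200 × 0.15) / 300 = 35/300 = 0.1167.
- Standard error under no difference: SE₀ = √[0.1167 × 0.8833 × (1/100 + 1/200)] = 0.0393.
- Standard error under the alternative: SE₁ = √[0.05 × 0.95/100 + 0.15 × 0.85/200] = 0.0334.
- Power = Φ[(0.10 − 1.96 × SE₀) / SE₁] = Φ(0.688) = **75.4%**.

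The stated figure is not reproduced.

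**Step 2. Exact power.** Summing Binomial(100, 0.05) × Binomial(200, 0.15) over all 101 × 201 possible results, and counting those where the Pearson test rejects, gives **76.9%**. A simulation of 1,000,000 trials also gives 76.9%.

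**Step 3. Why it falls short.** The Pearson test divides by a pooled standard error. With two thirds of participants in the arm with the higher rate, the pooled rate is pulled up to 11.67% and SE₀ exceeds SE₁. The ratio alone is not the cause; it matters which arm is larger. Exact power for the same 300 people:

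| Usual care / navigation | Exact Pearson power |
|---|---|
| 100 / 200 (planned) | 76.9% |
| 150 / 150 | 84.3% |
| 200 / 100 | 82.5% |

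These alternatives explain the gap; they are not proposals.

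**Step 4. Other methods at two-sided 5%, planned arm sizes.**

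| Method | Power |
|---|---|
| Chi-square with continuity correction, exact | 69.8% |
| Fisher's exact test | 74.7% |
| Pearson, exact | 76.9% |
| Arcsine formula | 80.3% |
| Likelihood-ratio chi-square, exact | 80.4% |
| Unpooled Wald, exact | 83.6% |
| Unpooled Wald, formula: Φ(0.10/0.0334 − 1.96) | 85.0% |

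Part of the gain of the likelihood-ratio and Wald tests comes from exceeding the nominal level. With a common rate of 5% in both arms, their true size is 5.6% and 6.1%, against 4.7% for Pearson.

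**Step 5. Range over the unstated level (exact Pearson).** Two-sided 2.5%: 67.4%. Two-sided 5%: 76.9%. Two-sided 6%: 80.4%. Two-sided 10%: 86.8%. One-sided 5%: 86.8%.

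**Step 6. Sensitivity to the assumed rates (exact Pearson, two-sided 5%).**

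| Usual care | Navigation | Power |
|---|---|---|
| 4% | 15% | 87.1% |
| 4.7% | 15% | 80.2% |
| 5% | 15% | 76.9% |
| 6% | 15% | 64.9% |
| 5% | 15.4% | 79.8% |
| 5% | 15.5% | 80.4% |

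**The case against.** The strongest reply is that the plan never commits to a two-sided 5% Pearson test. The hypothesis in section II is directional, and at one-sided 5% the claim is met with room to spare (86.8%). Even at two-sided 5%, a recognised formula such as arcsine gives just over 80%, so the figure has not been shown to be a slip in calculation. A mismatch between power method and planned test is one explanation; a different level or sidedness is another.

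Much of this stands. The documents do not show how the figure was obtained, and it can be derived in more than one way. It does not rescue the sentence as written. A directional hypothesis does not make a test one-sided, and VI.C plans an undirected test of a difference. Arcsine and Wald are not the Chi-square test as ordinarily understood. The likelihood-ratio form is a chi-square variant, but VI.C does not name it. The more conservative forms, continuity-corrected or Fisher's, fall further short.

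It is also fair to say that the gap is small beside the uncertainty in the inputs. A usual care rate of 4.7%, or a navigation rate of 15.5%, is enough to reach 80%. That sensitivity runs both ways, since power falls to 64.9% at a usual care rate of 6%. It limits the practical consequence and does not make the claim correct for 5% vs 15%.

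**Conclusion.** The concern holds, conditional on a two-sided 5% level and the uncorrected Pearson test. Under that reading the stated power is overstated: 76.9% exact, about 3 points below 80% (about 5 points by the normal formula). The risk of missing the target difference is about 23% (100 − 76.9). The conclusion would change if a one-sided 5% level, or a test or formula not named in the plan, was intended. In that case the fault is that the plan does not say so. The shortfall is modest and does not threaten the design, but the text should be corrected, since the figure cannot be checked and does not match the planned analysis under its ordinary reading.

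**What to change.** State the significance level, the sidedness and the form of the Chi-square test, and replace the power sentence in VI.D with something like:

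> With 200 and 100 participants and a two-sided 5% Pearson Chi-square test, power is about 77% for 15% vs 5%, and about 80% for 15.5% vs 5%.

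If another test or level was intended, name it in both VI.C and VI.D so that the power figure and the analysis agree.

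The cost is a small edit to the text and a slightly less favourable figure. Enrolment, allocation and endpoints stay as they are.
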